Study protocol cover page

Official study title: Multicenter registry to study the characteristic and outcomes of Jordanian Heart Failure patients

The Jordanian Heart Failure Registry (JoHFR)

NCT04829591

The actual document date and approval date 30/3/2021

The updated document date 17/4/2021

A Multicenter Registry to Study the Characteristics and Outcomes of Jordanian Heart Failure Patients. The Jordanian Heart Failure Registry (JoHFR)

ClinicalTrials.gov Identifier: NCT04829591

(Study protocol)

Principal investigator and study chair : [name] , MD , MSc , FACC , FSCAI .

Principal investigator: [name].

Brief Summary

Heart Failure research registry is a collection of computerized information about individuals with heart failure. The database in this registry is obtained from several Jordanian medical centers which will represent an extremely valuable resource for epidemiological research on heart failure patients.

Detailed Description:

Understanding the cause of Heart Failure (HF) and how the body will respond to it, is critical for an effective treatment. HF is a global problem with significant morbidity and mortality, despite improved understanding of the pathophysiology and a growing range of therapeutic options. Jordanian Heart Failure Registry (JoHFR) will be the first research project of heart failure prevalence in Jordan. It is undertaken by primary healthcare professionals with main aim to improve knowledge about the care of patients with HF. The investigators responsible for conducting this research are physicians and their teams who deal with heart failure patients in their outpatient and inpatient clinic centers including the public and private medical sectors in Jordans' medical community . Standards in the Hashemite kingdom of Jordan complies with the recognized good guideline directed medical practices internationally.

Objectives of the registry:

Up to date, there is still a lack of reliable pathology data that summarizes patient cases with heart failure disease. This research aims to fill this gap and provide the local and international medical communities with this important set of comparative data in order to determine our current situation in regards to screening, management, and follow up of patients. This will have a direct impact on improving Heart Failure patient outcomes by directing our focus on strengths and weaknesses in our management in this ongoing high morbidity and mortality syndrome. Furthermore, this registry will focus on describing the diagnostic and therapeutic approaches undertaken by cardiologists in their care of patients with HF in order to improve future management

of patients with high HF risks. The prevalence of the clinical profiles of patients with acute and chronic HF will also be evaluated.

Study design and methodology:

- This registry consists of multiple variables including demographics, concomitant diseases, diagnostic procedures, hemodynamics, laboratory data, and medications used, discharge information and instructions. The patient information is detailed in the attached questionnaire (appindex1) which will be filled by participating who will record details of their HF patients and transfer these data for documentation.
- This study aims to include sufficient number of patients with Heart Failure and is expected to last for extended time until the study sample is completed by participating healthcare professionals. The data collected at 12 months will be the basis of the initial statistics, upon which the trial duration will be determined.
- The principal research coordinator and his team will train personnel of the participating units on how to register patients and how to use the registry.
- Patient safety, security and confidentiality will be retained at all times during the course of the study and thereafter.

• Follow up after one year should include data on morbidity (including Heart failure hospitalization) and mortality with detailed information on medications, quality of life, and functional capacity. • The study will comply with the ethics of research and (IRB) institutional review board approvals and any other required official organizational requirements.

Inclusion and exclusion criteria:

- Inclusion criteria:
 - 1. Patients who are 18 years or older with Heart Failure diagnosis as defined by internationally recognized guidelines.
 - 2. Current residents of the Hashemite Kingdom of Jordan.
- Exclusion criteria:
 - 1. Patients who refuse or unable to sign a consent form.
 - 2. Patient inability to follow up with provider

Statistical analysis:

Data will be pooled and descriptive and comparative statistical tests will be used to categorize the patients based on the disease sub-typing and management quality and to find the prevalence of heart failure disease different types, classes and stages amongst Jordanians. Furthermore, comparative analysis will be performed to test the efficiency, accuracy, and the quality of medical practice in Jordan. Statistical analysis will be done using SPSS V21. See appindex1 below.

Annindex1.

	Patient Initials/Site number:
DOB: / / (MM/DD/YYYY) Gender: M F Admission date/ Office visit / / :	
Discharge Date/Time / / :	

Medical History (Select all that apply):

□ H/O ASCVD	Implanted devices	□ Notes :
□ H/O Arrhythmias	History of structural heart disease	
	Other relevant medical history	
□ ASCVD risk factor:		
🔷 🕹 DM		
ITN		
Smoking		
Alcohol Abuse		
🔷 🗘 Dyslipidemia		
Obesity		
 Positive family history of premature ASCVD 		
🔷 🗘 CKD		
Others.		
	Heart Failure History	
Etiology:	□ Ischemic/CAD	Non-Ischemic
Check if history of :		Hypertensive
		Alcohol/Other Drug
		Chemotherapy
		□ Viral
		Postpartum

	□ Familial
	Other Etiology
	Unknown/Idiopathic

Known history of HF prior to this admission?	⊖ Yes	o No
--	-------	------

# of hospital admissions in past 6 mo./office visit for HF:	0	2 >2	o Unknown
	Medications Used Prior t	o Admission: [Select all that ap	oly]

Symptoms	Dyspnea		Palpitations
(Closest to Admission) Select all that apply	NYHA class (, , , V) ❑ Orthopnea	 PND Fatigue Chest pain 	

Vital	signs

(Closest to Admission/Office visit)

Heart Rate	Heart Rate bpm	□ Reg □ irreç	
Examination	JVP: O Yes	0 No	
(Closest to Admission/Office visit)	Rales: o Yes	o No	
	Lower Extremity o Yes Edema	• No	
Lipids	TC: LDL: HDL: _ mg/dL mg/dL	TG: mg/dL	□ Lipids Not Available
Labs Closest to Admission)/ office visit	Na	⊖ mg/dL	□ Unavailabl e
	BNP	⊖ ng/L	□ Unavailabl e
	К	⊖ mg/dL	□ Unavailabl e
	Hb	⊖ g/dL	□ Unavailabl e
	Albumin	⊖ g/dL	□ Unavailabl e
	NT-proBNP	⊖ ng/L	□ Unavailabl e
	SCr	⊖ mg/dL	□ Unavailabl e

eGFR	 ○ ml/min/ 1.73m² 	
BUN	⊖ mg/dL	□ Unavailabl e
Troponin (Peak) ng/L �� T quantitative / Hs �� I	NormalAbnormal	□ Unavailabl e
Ferritin ng/mL		
Transferrin saturation HbA1C %	Unavailable	

Fasting Blood Glucose (mg/dL)	Unavailable
EKG QRS	Unavailable

	Duration (ms)			
	EKG QRS Morphology	Normal	RBB B VCD	PacedUnavailable
Procedures				

No Procedures	Atrial Fibrillation Ablation or Surgery
Cardiac Cath/Coronary Angiography	Cardiac Valve Surgery
Coronary Artery Bypass Graft	□ Cardioversion
CRT-P (cardiac	CRT-D (cardiac resynchronization therapy
resynchronizationtherapy pacing only)	with ICD 🖵 Intra-aortic Balloon Pump
 Dialysis or Ultrafiltration ICD only 	Left Ventricular Assist Device
Mechanical Ventilation	Pacemaker
Right Cardiac Catheterization	

EF	- By Echo - By other means %	Obtained:	 This Admission Within the last year > 1 year ago
Added Oral Medications during hospitalization Select all that apply	□ None □ ARNI □ ARB	 Aldosterone Antagonist Hydralazine Nitrate 	 ACE Inhibitor Beta Blocker
Parenteral Therapies during hospitalization Select all that apply	 None Dopamine Iron Milrinone 	 Nitroglycerine Other IV Vasodilator 	 Dobutamine Loop Diuretics Intermittent Bolus Continuous Infusion

Was the patient ambulating at the end of hospital day 2?	Yes No	Not Documented	
---	--------	----------------	--

Was DVT prophylaxis initiated by the end of hospital day 2?	Yes No	Contraindicated
---	--------	-----------------

lf yes,	 Low dose unfraction Low molecular (LMWH) Warfarin Other 		 Factor Xa Inhibitor Direct thrombin inhibitor Intermittent pneumatic compression devices (IPC)
Discharge Date/Time / / :	1		MM/DD/YYYY only
Primary Cause of Death	 Cardiovascular 	Non-Cardiovascular	 O Unknown
If Cardiovascular:	 Acute Coronary Syndrome 	 ○ Worsening Heart Failure 	 Sudden Death Other
When is the earliest documen measures only?	tation of comfort	Day 0 or 1 Day 2 or after	 Timing unclear Not Documented

Symptoms (closest to discharge)	WorseUnchanged	Better, Symptomatic Better, Asymptomatic	Una Una	able to determine
Vital Signs (closest to Discharge)	Weight ᡇ	₩¥¥¥		ot Documented
	Heart Rate Bpm regula	r Irregular	□ N	ot Documented
	BP-Supine _ / _ mmHg (systolic/diastolic)	□ N	ot Documented
	Respiratory Rate breaths	s per minute		
Exam (Closest to Discharge)	JVP:○ Ye	s o No	o Unknow n	
	Rales: o Yes		0 1	lo

	Lower Extremity o Yes Edema	0 N	10
Labs (Closest to Discharge)	Na	∘ mg/dL	Unavailable

BNP	o mg/dL	🗅 Unava	ailable
SCr	o mg/dL	🗅 Unava	ailable
BUN	o mg/dL	🗅 Unava	ailable
NT-BNP (pg/mL)		ot Documente	ed
κ _ο mEq/L	o mmol/L	∘ mg/dL	
eGFR	** N 1.7:		MDRD

Angiotensin Converting Enzyme Inhibitor (ACEI)		
Prescribed?	∘ Yes ∘ No	Frequency:
If Yes, Medication: Dosage:		
Beta-Blocker		

Name:	Dose:		
	Aldosterone Antagonist		
	Medication: Dosage:	Frequency:	
Anti-hyperglycemic Medications:			
Name:	Dose:		
Lipid Lowering Medication(s):			
Name:	Dose:		
Hydralazine Nitrate			

Name:	Dose:
	Other Medications at Discharge
☐ Antiarrhythmic ☐ Amiodarone ☐ Sotalol ☐ Other	 Ca Channel Nitrate Blocker Ranolazine Digoxin Other Anti-Hypertensive Diuretic Other Loop Diuretic Thiazide Diuretic

Angiotensin Receptor Blocker (ARB)				
Name:	Dose:			
Angiotensin Receptor Neprilysin Inhibitor (ARNI)				
Name:	Dose:			
	Acetylsalicylic acid (ASA)			
Name:	Dose:			
	Anticoagulation Therapy			
Prescribed?	Yes No	Dosage		
lf Yes,	Class:			

Warfarin	

Clopidogrel		
Prescribed?	∘ Yes ∘ No	

If Yes,	Dosage: Frequency:		
	Other Antiplatelet(s)		
Name:	dose:		
Activity	\circ Yes \circ No Diet (Salt restricted)	∘ Yes	∘ No
Follow-up	\circ Yes \circ No Medications	∘ Yes	• No
Symptoms Worsening	\circ Yes \circ No Weight Monitoring	∘ Yes	o No
Follow-up Visit Scheduled	 ○ Yes ○ No Date/Time of first follow up visit: 	//:	-
Location of first follow-up vis	i t: �� Office Visit �� Home Health Visit	TelehNot Doc	

Medical or Patient Reason for no follow-up		• No	
appointment being scheduled	 Yes appointment being scheduled? 		
	Follow up visits form:		
Scheduled at:	3 months 6 months	12 months	
NYHA class: (, , , V)			

eGFR:			
Loop diuretics (name,dose):			
Vital signs			
	New EF ,method, if a	ny :	
CV related hospital admission:	C Yes:	□ Yes:	G Yes:
	□ WHF		□ WHF
		□ WHF	□ ACS □ Arrhythmias
	Arrhythmia		
	S	Arrhythmia	No
		S	
	Others	□ Others	12 months

No	
3 months 6 months	

Labs:	
Meds:	

Other notes:

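### The protocol does not say how eligible patients are selected for entry or count those left out, yet it plans prevalence and quality-of-care statements about Jordan as a whole

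*Protocol*

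**What the plan says.** Under Study design and methodology, the protocol says that the questionnaire is completed by participants "who will record details of their HF patients and transfer these data for documentation". The noun naming these participants is missing from the sentence. The same section sets the size and length of enrolment loosely: "This study aims to include sufficient number of patients with Heart Failure", and the study "is expected to last for extended time until the study sample is completed by participating healthcare professionals". The coordinating team "will train personnel of the participating units on how to register patients and how to use the registry".

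The Inclusion and exclusion criteria define who is eligible: "Patients who are 18 years or older with Heart Failure diagnosis as defined by internationally recognized guidelines", and resident in Jordan. They exclude "Patients who refuse or unable to sign a consent form", and also patients who cannot follow up with their provider. These rules say who may be entered. They do not say which eligible patients must be entered.

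The Statistical analysis section then states what the data are for: "to find the prevalence of heart failure disease different types, classes and stages amongst Jordanians". It adds that "comparative analysis will be performed to test the efficiency, accuracy, and the quality of medical practice in Jordan".

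**The concern.** Both planned outputs are largely proportions: the share of patients in each type, class and stage, and the share receiving particular elements of care. Such a proportion describes the people entered. It describes a wider group only if entry is unrelated to the feature counted, or if the relation is known.

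The protocol secures neither condition. A centre could enter every eligible patient, every second one, mainly admitted patients or mainly clinic attenders, and comply in each case. The questionnaire runs from admission to discharge or cause of death. It includes care items such as early ambulation, thrombosis prophylaxis, discharge medication and follow-up scheduling. Nothing fixes when in that course a patient is entered, so the plan does not rule out entry after care or outcome is known.

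At stake is whether the reported mix of heart failure and the reported quality of care describe patients at these centres or only those who happened to be registered.

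**Working it through.** **1. Search for a selection rule.**

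| Item | In the protocol? |
|---|---|
| Eligibility criteria | Yes |
| Consecutive or all-eligible entry | No |
| Sampling frame or recruiting window | No |
| Target number | No figure, only a sufficient number |
| Log or count of eligible patients not entered | No, and the questionnaire has no field for it |
| Training of site staff | Yes, on registering patients and using the registry; it does not say which patients, and no manual is cited |

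**2. Compare with the inference.** The Brief Summary says that the data come from several Jordanian medical centres. The Statistical analysis section words its results for Jordanians and for practice in Jordan. Two steps are uncovered: from patients entered to eligible patients at a centre, and from those centres to the country.

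**3. Size of a possible distortion.** The protocol states no rate, share or sample size, so there is no figure to reproduce. All inputs here are assumptions:

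- p: true share of eligible patients with the feature (0.3, 0.5, 0.7).
- r: probability of entry for patients with the feature, relative to those without it (0.5 to 2).

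Expected share in the registry = p·r / (p·r + 1 − p).

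For p = 0.5:

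- r = 0.5: 0.25 / (0.25 + 0.5) = 0.333
- r = 1: 0.5 / (0.5 + 0.5) = 0.500, no bias
- r = 1.25: 0.625 / (0.625 + 0.5) = 0.556
- r = 1.5: 0.75 / (0.75 + 0.5) = 0.600
- r = 2: 1.0 / (1.0 + 0.5) = 0.667

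| True share | r = 0.5 | r = 1 | r = 2 |
|---|---|---|---|
| 30% | 18% | 30% | 46% |
| 50% | 33% | 50% | 67% |
| 70% | 54% | 70% | 82% |

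**4. Compare with sampling error.** The 95% half-width for a 50% share is 1.96·√(0.25/N). For assumed N of 500, 1000 and 2000 it is 4.4, 3.1 and 2.2 percentage points. At r = 1.25 the bias is 55.6 − 50 = 5.6 points, more than the half-width at each of these sizes. N does not appear in the formula of step 3, so more patients narrow the interval around the same biased value.

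**5. What a denominator would add.** If a centre enters a fraction c of its eligible patients and the share among those entered is s, the share among all its eligible patients must lie between c·s and c·s + (1 − c). The width of that range is 1 − c. Without a count of those not entered, c is unknown and no such bound can be given.

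**The case against.** The strongest reply is that the protocol is silent on selection and does not prescribe a bad method. Participants who record their heart failure patients may be recording all of them, and training on how to register patients is a natural place for such an instruction. This is a fair reading, and it rules out some stronger ones. A reader might infer that the treating clinician picks whom to enter and is then judged on those patients. The text does not say so: the sentence lacks the noun that would show who completes the form, and elsewhere the protocol speaks of physicians with their teams and of trained unit personnel. A reader might also infer that care will look better than it is. Nothing in the document gives a direction, since sites could as easily enter sicker or more complex patients.

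The silence still matters. Enrolment ends at a sufficient number, which does not describe a census, and the training text does not say which patients to register. Selection for entry is a rule that sites apply during enrolment, so it belongs in the protocol.

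A second reply is that analysis can help. This is partly right, and it would be too strong to say that nothing can be repaired. Adjustment for recorded characteristics, comparison between centres and sensitivity analysis can reduce or explore the problem. They cannot deal with unrecorded reasons for entry, and they cannot supply a denominator that was never collected.

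A third reply is that consecutive entry would not make the centres representative or bring back patients excluded for consent or follow-up. That stands, and it limits what the fix can claim.

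**Conclusion.** The point holds as a gap between how patients enter the registry and what the registry is meant to show. The protocol sets no selection rule and no count of patients left out, and it words its conclusions for the whole country. Selective entry could bias the planned proportions upwards or downwards. With an assumed true share of 50% and a relative entry probability between 0.5 and 2, the reported share would run from 33% to 67%, with no bias at 1. These values are illustrative. The document gives no information on the actual size or direction, and it does not show that selection has taken place.

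A reader should not conclude that the registry's results will be wrong, or that consecutive entry alone would support national statements. The supported conclusion is narrower: a centre can follow the plan as written and produce proportions with a selection error that nobody can later measure.

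**What to change.** - Add a rule that each centre registers every consecutive eligible patient. Where volume is high, allow instead all eligible patients in recruiting weeks fixed in advance by the coordinating team.
- Keep a minimal log, approved by the IRB, of eligible patients not entered: age, sex, setting and reason. The reasons should include consent refused, unable to consent and unable to follow up.
- Report the capture rate by centre beside the main results.
- Word the conclusions as applying to eligible heart failure patients at participating centres, not to Jordanians in general, because centres are not sampled and the exclusions remain.

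The cost is a short protocol change, modest site workload (limited by fixed recruiting weeks) and ethics approval, since the log would hold data on people who have not consented. The log should start with enrolment because it is hard to rebuild afterwards. No patient's treatment is affected.

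### The analysis refers heart failure type, class and stage shares to Jordanians, but the registry supports shares among enrolled patients at participating centres only

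*Protocol*

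**What the plan says.** Two statements set a national target.

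- Protocol, Statistical analysis: data are pooled and tests are used to categorise patients and "to find the prevalence of heart failure disease different types, classes and stages amongst Jordanians". The next sentence plans comparisons to judge the quality of medical practice, again for the country as a whole.
- Protocol, Detailed Description: the registry "will be the first research project of heart failure prevalence in Jordan".

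Other parts of the protocol say who enters.

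- Brief Summary: the data are "obtained from several Jordanian medical centers".
- Detailed Description: the investigators are physicians and their teams "who deal with heart failure patients in their outpatient and inpatient clinic centers", "including the public and private medical sectors".
- Study design and methodology: the form is completed by participants "who will record details of their HF patients and transfer these data for documentation".
- Inclusion criteria: "Patients who are 18 years or older with Heart Failure diagnosis" and "Current residents of the Hashemite Kingdom of Jordan".
- Exclusion criteria: patients who refuse or cannot give signed consent, and patients who cannot be followed up by the provider.

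The title, the main aim and the objectives take HF patients as the reference group. The objectives use the word prevalence only for clinical profiles among patients with acute and chronic HF.

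**The concern.** The stated target decides what the registry may conclude. As worded, a share computed among enrolled patients could be published as the share among all HF patients in Jordan. The route into the registry does not by itself support that step. The protocol describes no rule for choosing centres, no catchment population, no consecutive or random enrolment and no weighting.

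Pooling adds to the problem. Patients enter from admissions and from office visits, and these two groups may well differ in functional class and stage. A pooled figure then depends partly on how many of each happen to be recorded. The protocol presents the registry as the first of its kind in the country and names no earlier national figure against which such a result could be checked.

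**Working it through.** The protocol states no sample size, precision target or expected share, so there is no figure to reproduce. The check compares each stated target with the data described.

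**1. HF prevalence in Jordan (Detailed Description).** Prevalence = HF cases / persons in the population. Inclusion criterion 1 admits only people who already have the diagnosis, so every record belongs to the numerator. No catchment, census or screened population is described for the denominator. The quantity cannot be estimated from these data, whatever analysis is specified later. No analysis of it is planned either, so the phrase is wrong but drives no calculation.

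**2. Shares of types, classes and stages (Statistical analysis).** The natural reading is case mix: patients of a given type / all HF patients. On that reading the registry does have a denominator, namely enrolled patients. What remains is the step from enrolled patients to Jordanians:

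| Named target | Who is in the data |
|---|---|
| Jordanians | Residents of Jordan, whatever their nationality |
| The country | Several centres, public and private, with no selection rule stated |
| All with HF | Diagnosed adults who consent and can be followed up |
| All such patients | Those whom participating providers record |

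**3. When the two shares agree.** Let s be the share of a class among all HF patients in Jordan, and k the chance of enrolment for that class relative to the others. The expected share among enrolled patients is

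p = s·k / (s·k + 1 − s).

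Setting p = s gives k = s·k + 1 − s, so k(1 − s) = 1 − s and k = 1. The shares agree only if enrolment does not depend on class. Sample size does not appear in the formula, so recruiting more patients narrows the interval without moving p towards s.

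An illustration with assumed values: for s = 30% and k = 0.8, p = 0.24 / 0.94 = 25.5%. The 95% interval, p ± 1.96·√(p(1 − p)/n), is 21.7–29.4% at n = 500 and 23.6–27.4% at n = 2000. At k = 1, p = 30%. The protocol gives none of s, k or n. The example shows how the formula behaves and says nothing about the size of any bias in this registry.

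**4. Pooling over entry setting.** With w the fraction of enrolled patients who enter as inpatients, the pooled share is w·p(in) + (1 − w)·p(out). Unless p(in) = p(out), it depends on w, which follows from which centres and clinics take part. Reporting the two components removes that dependence.

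**5. Can the form separate the settings?** In Appendix 1 the admission date and the office visit stand on one combined line, which does not by itself show which applied. The form also has a discharge date and items that make sense only during a hospital stay: therapies given in hospital, and ambulation and thrombosis prophylaxis by hospital day 2. Together these may identify setting, but the protocol does not say so.

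**The case against.** The strongest reply is that this is largely wording. The title names HF patients, the main aim is knowledge about their care, and the objectives list no population prevalence. A reader of the whole document is unlikely to expect a national prevalence figure. A target wider than the sample is normal for a voluntary multicentre registry, and limits on generalising can be handled when results are reported. The protocol does not claim that its sample is representative.

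Much of this stands. It disposes of any suggestion that the registry sets out to estimate national HF prevalence and will fail. It also keeps the severity low. It does not rescue the Statistical analysis sentence, which is the operative statement of what will be estimated and which names Jordanians.

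A reader might go further and infer that enrolment is selective, or that the shares will be biased in a known direction. The documents do not support that. Consecutive enrolment is not stated, but site personnel are to be trained in how to register patients and those instructions are not shown. The consent and follow-up exclusions could remove sicker patients, while recruitment of inpatients could add them. The net effect is unknown. Coverage of both public and private sectors speaks for breadth, though it is not a sampling frame.

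**Conclusion.** The point holds and is minor to moderate. The Statistical analysis section is wrong as written: pooled registry data give shares among enrolled HF patients, and these are national shares only if enrolment is unrelated to type, class and stage, which nothing in the protocol secures. The next sentence, on quality of medical practice, has the same overreach. The prevalence phrase in the Detailed Description is a wording error.

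No stated calculation is affected. No bias has been shown, and its direction and size cannot be derived from the protocol. The severity therefore rests on the mismatch between target and enrolled group, not on the assumed figures above. The conclusion depends on the enrolment route being as the protocol describes it.

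**What to change.** 1. In Statistical analysis, state the target as *the distribution of heart failure types, classes and stages among enrolled HF patients resident in Jordan at participating centres*.
2. Limit the following sentence, on quality of medical practice, to participating centres in the same way.
3. Report the shares separately for inpatient and outpatient entry as well as pooled. Take setting from the admission/office-visit line together with the discharge date and the hospital-stay items already on the form. The sponsor should confirm that these separate the two settings. If they do not, mark on the existing line which one applies.
4. In the Detailed Description, replace the prevalence phrase with *a registry of the characteristics and outcomes of HF patients in Jordan*.

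The cost is three reworded sentences, slightly more tabulation, possibly a mark on an existing line of the form, and a narrower claim.

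### The protocol promises the prevalence of HF types, classes and stages among Jordanians, but its design supports only their distribution among the HF patients enrolled, and an overall figure can move with the inpatient/outpatient mix.

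*Protocol*

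**What the plan says.** The Statistical analysis section states: "Data will be pooled and descriptive and comparative statistical tests will be used". The groupings it names are disease sub-type and quality of management, and it gives the purpose as "to find the prevalence of heart failure disease different types, classes and stages amongst Jordanians". The Detailed Description makes a similar claim, that the registry "will be the first research project of heart failure prevalence in Jordan".

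On who is enrolled, the Detailed Description says the investigators see patients "in their outpatient and inpatient clinic centers including the public and private medical sectors". The Brief Summary says the data come from several Jordanian centers. Study design and methodology gives the size only as a sufficient number, with no quota by setting, no sampling frame and no rule for consecutive enrolment. The eligibility criteria require an HF diagnosis and exclude patients who refuse or cannot give consent and those who cannot be followed up.

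The nearest thing to a split by setting is in Objectives of the registry: "The prevalence of the clinical profiles of patients with acute and chronic HF will also be evaluated".

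Appendix 1 uses one form for both settings, with the shared header field "Admission date/ Office visit". The vital signs and examination blocks carry the label "Closest to Admission/Office visit", and the baseline laboratory block also names the office visit. The symptom block that holds NYHA class reads, as shown, "Closest to Admission) Select all that apply", with no mention of an office visit.

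**The concern.** Two things are at stake.

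The first is the claim. A prevalence among Jordanians needs either a denominator of Jordanians or, read more loosely as a proportion within HF, a sample that represents Jordanian HF patients. The protocol describes neither.

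The second is what an overall figure means. Admitted patients and office patients may differ in functional class and stage. If they do, a single percentage averages two populations with weights set by whoever the participating physicians happened to enrol. Objectives of the registry wants data that local and international readers can compare. A difference from another registry could then reflect case mix and not disease or care.

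The NYHA label matters in a smaller way. Class is one of the quantities to be reported, and for a patient enrolled at an office visit the block as shown names no time point.

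**Working it through.** The protocol gives no prevalence, sample size or precision figure, so there is nothing to reproduce. The check is a comparison of target with design, followed by an illustration.

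**1. Target against design**

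| Needed for the stated target | What the protocol provides |
|---|---|
| A denominator of Jordanians | HF patients only (eligibility criteria) |
| Or a representative sample of Jordanian HF patients | Several participating centers; no sampling frame or consecutive-enrolment rule |
| A known or fixed mix of settings | Both settings enrol; no quota or ratio |
| No selection related to severity or access | Patients unable to consent or follow up are excluded |

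The quantity the design can estimate is the distribution of types, classes and stages among enrolled HF patients.

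**2. Dependence on mix**

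Let w be the inpatient share of the sample, and let p_in and p_out be the proportions in NYHA III-IV in each setting. Then:

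- overall proportion = w × p_in + (1 − w) × p_out
- change per 0.10 of w = 0.10 × (p_in − p_out)

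All values of w, p_in and p_out below are assumptions.

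| p_in, p_out | w = 0.20 | w = 0.40 | w = 0.60 | w = 0.80 | Change per 0.10 of w |
|---|---|---|---|---|---|
| 0.70, 0.30 | 0.38 | 0.46 | 0.54 | 0.62 | 0.04 |
| 0.60, 0.40 | 0.44 | 0.48 | 0.52 | 0.56 | 0.02 |
| 0.50, 0.50 | 0.50 | 0.50 | 0.50 | 0.50 | 0 |

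For example, the first cell is 0.20 × 0.70 + 0.80 × 0.30 = 0.14 + 0.24 = 0.38.

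**3. Does sample size help?**

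The worst-case 95% half-width is 1.96 × √(0.25/n). For assumed n of 500, 1,000 and 5,000 it is 4.4, 3.1 and 1.4 points. A larger registry narrows the interval around the mixed figure but leaves its dependence on w unchanged.

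**4. Can setting be recovered from the form?**

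Usually. Besides the shared header field, Appendix 1 collects a discharge date, oral and parenteral treatments given during the hospital stay, two hospital-day-2 items, and signs and labs nearest discharge. Taken together these will normally identify an inpatient, so a split by setting is feasible with data already planned.

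**The case against.** The strongest reply is that reporting by subgroup belongs in a statistical analysis plan, which may exist and is not shown. That stands: the absence of a stated split is not in itself a fault, and nothing in the protocol forbids one. In a multicenter registry, pooling may also mean only combining centers, so a single figure across settings is an inference and not something the text commits to. What the reply does not answer is the national target, which is written in the protocol itself.

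Prevalence is also only one of several aims. The Detailed Description gives the main aim as better knowledge of HF care, and acute and chronic profiles are planned too. This limits the weight of the point. But acute versus chronic is a clinical split that probably overlaps with setting without being the same, and it fixes no mix.

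The magnitudes are arithmetic on assumed rates. The range includes no effect, and the widest shift (38% to 62%) needs the inpatient share to run from 20% to 80%. That is a fair limit on the evidence.

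Three stronger readings are tempting, and the documents support none of them:

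- *That the form fails to capture setting.* The extracted form is damaged, a tick box may have been lost, and other items usually reveal the setting.
- *That NYHA class for office patients will be unusable.* The header date makes the index contact the evident time point, and class is collected again at 3, 6 and 12 months. The label is an inconsistency and not a demonstrated loss of data.
- *That a split by setting would yield national figures.* It would not. Setting-specific figures would come from the same selected centers and consenting patients.

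**Conclusion.** The point holds in limited form. The protocol states a national prevalence target that its enrolment cannot support. As written, it supports a description of enrolled HF patients.

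Any overall frequency that differs between inpatients and outpatients also moves with the enrolled mix: by 4 points per 10 points of inpatient share under an assumed 70% versus 30%, by 2 points under 60% versus 40%, and not at all if the settings are alike. The mismatch between target and design rests on the text alone. The size of the mix effect rests wholly on assumed rates.

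The NYHA/symptom label differs from its neighbouring blocks as shown and is worth aligning. Severity is minor to moderate, because the remedy is mostly wording and the data for a split are largely collected already.

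**What to change.** 1. In Statistical analysis, replace the national prevalence target with the distribution of HF types, classes and stages among enrolled HF patients. Make the matching change in the Detailed Description.
2. State there, or in the analysis plan, that class, stage and type are reported separately by enrolment setting (inpatient admission or office visit). Derive setting from the header field, the discharge date and the hospital-only items. Give any overall figure as secondary, alongside the inpatient share.
3. Label the symptom/NYHA block "Closest to Admission/Office visit", as the vital signs and examination blocks already are.
4. Add an explicit setting tick box only if the original form has none.

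The cost is a few sentences, one label, possibly one form item, and a chart check for any record whose setting stays unclear. The claim becomes more modest and the groups smaller. If an assumed 1,000 patients split evenly, the worst-case half-width goes from 3.1 points overall to 4.4 points per setting. No new patients are needed. Reporting by setting removes the dependence on mix but does not make the figures national, so the rewording in step 1 is needed either way.
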